3.1.5 Handling of Dropouts and Missing Data

In general, data will be analyzed and presented as observed and will not be imputed for the analysis of efficacy and safety.

In case the start and end dates for adverse events and concomitant medications/procedures are missing or incomplete, the missing component(s) will be assumed as the most conservative value possible. For example, Adverse Events (AEs) with missing start dates, but with stop dates either overlapping into the treatment period or missing, will be counted as treatment-emergent, taking the worst-case approach. When partial dates are present in the data, both a partial start date and/or a partial stop date will be evaluated to determine whether it can be conclusively established that the AE started prior to the start of study treatment or ended prior to the start of study treatment. If the above cannot be conclusively established based on the partial and/or present dates, then the AE will be considered as treatment-emergent. Actual data values as they appear in the original case report forms (CRFs) will be presented in the data listings.

If a medication has incomplete start or stop dates, dates will be imputed to determine whether a medication should be considered prior or concomitant. If a medication start date is incomplete, the first day of the month will be imputed for missing day and January will be imputed for missing month. If a medication stop date is incomplete, the last day of the month will be imputed for missing day and December will be imputed for missing month. Incomplete start and stop dates will be listed as collected without imputation.

3.1.6 *COVID-19 pandemic*

The COVID-19 pandemic may impact the conduct of the study from different aspects including quarantines, site closures, travel limitations, interruptions to the supply chain for the investigational product, or other considerations if site personnel or trial patients become infected with COVID-19. Study procedures affected by the COVID-19 pandemic are recorded, as are reasons for study discontinuation/screen failure, protocol deviations, and adverse events. All such data will be listed, and any summaries of this data are mentioned below.

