3.4.1 Primary Endpoints

3.4.1.1 Adverse Events (AEs)

AEs will be captured from the date of informed consent through study completion. All AEs will be coded to system organ class and preferred term using the MedDRA version 22.0 and analyzed using the Safety Population. A treatment-emergent adverse event (TEAE) is defined as an adverse event with a start date and time on or after the first administration of study drug and up to 30 days past the last administration of study drug, or after 30 days past last dose and meeting one of the following criteria:

- Serious AE (SAE)
- AE of special interest post-transplant
- AE related to study medication
- AE related to HLA sensitization

Adverse events of special interest post-transplant are graft rejection, CMV syndrome, and CMV disease.

An overview of AEs will be provided including counts and percentages of patients with the following:

- Any AEs
- Any TEAEs
- Any Grade 3 (severe) or higher TEAEs
- Any Grade 3 (severe) or higher TEAEs related to study medication

- Any TEAEs related to study medication
- Any TEAEs of special interest post-transplant
- Any TEAEs of special interest post-transplant and related to study medication
- Any serious AEs (SAEs)
- Any treatment-emergent serious AEs (TE-SAEs)
- Any TEAEs leading to discontinuation of study medication
- Any TEAEs related to study medication leading to discontinuation of study medication
- Any TEAEs related to COVID-19
- Most frequently reported adverse events related to study medication

Both the pre-transplant and post-transplant adverse events and adverse events of above categories will be included in the table summary. The post-transplant adverse event will be summarized by treatment group for Groups 1 and 2 and open-label HB-101 for Group 3.

Counts and percentages of patients will also be presented by system organ class and preferred term for each of the categories in the overview. Counts and percentages of most frequently reported adverse events and most frequently reported adverse events related to study medication may also be displayed in separate tables.

Listings will be presented specifically for SAEs and TEAEs leading to discontinuation of study drug.

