3.4.1.4 Immunogenicity

To assess the immunogenicity of HB-101, descriptive central statistics will be presented for the following immunogenicity parameters using the Immunogenicity Population:

- CMV neut
- CMV ELISPOT pp65
- CMV ELISPOT gB

The summary will also be based on the number of doses of medication or placebo received (only for 2 and 3 doses). For CMV ELISPOT pp65, CMV ELISPOT gB, and the combination of CMV ELISPOT pp65 and gB, counts and percentages of positive responses will be displayed in addition to the descriptive central statistics. A Wilcoxon signed-rank test will be performed by each treatment and dose group versus the Pre-Dose 1 values from that group. A Mann-Whitney U test of HB-101 versus the corresponding Placebo at each time point will also be performed. The CMV neut parameter will undergo all tests and summaries of the other parameters with the

addition of a 95% confidence interval of the geometric mean titer and a categorical summary of the increase of titer result from Pre-Dose 1 based on the following ranges:

- >2-fold
- >3-fold
- >4-fold

The CMV neut parameter summarization will also be repeated by viremia status (with or without) at Pre-Dose 1 (Group 3 only) and day of transplant.

The result of CMV ELISPOT pp65, CMV ELISPOT gB, pp65 together with gB, and CMV neut result will be plotted against the time of dose received and day of transplant by study medication, dose, and group. The boxplot of CMV neut result by treatment and dose will be provided. The plot of seroconversion rates by dose and treatment will be plotted against the time of dose received and day of transplant. The CMV neutralization antibody titers (NTA) responses and CMV viremia will be plotted by treatment, dose, and viremia status against the time of dose received and day of transplant.

The pre- and post-transplant immunosuppressant use will be summarized by preferred term for all post-transplant randomized patients.

The CMV serology information will be summarized for transplant recipient and kidney donor.

For patients who developed HLA sensitization, the pre- and post-dose sample and recipient genotype information will be listed.

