3.4.2.1 Secondary Endpoint Definitions

- CMV infection is defined as quantifiable local CMV PCR test results above the lower limit of quantification (LLOQ).
- CMV syndrome is defined as CMV infection with at least one syndrome symptom present.
- CMV syndrome disease is defined as CMV infection with (CMV syndrome OR at least one end-organ disease category present).

- CMV infection requiring anti-viral therapy is defined as the triggered start of anti-virals as entered on Local CMV PCR results CRF.
- Time to infection is defined as the date of the first quantifiable result above LLOQ – transplant date.
- Duration above LLOQ is the number of consecutive days with a quantifiable result above LLOQ, starting with the first such value.
- Anti-viral therapy use is defined as the recorded use of flagged anti-viral therapies on the concomitant medication CRF following the triggered start of anti-virals as entered on the Local CMV PCR results CRF.
- Time to anti-viral therapy use is defined as the date of the first post-transplant anti-viral use – transplant date.
- Duration of anti-viral therapy use is the total number of days of recorded post-transplant anti-viral use.
- Number of anti-viral therapy courses is the sum of unique recorded post-transplant anti-viral entries on the concomitant medication CRF.
- Time to rejection is defined as first date of biopsy with rejection recorded – transplant date.

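### The partial-date rule for adverse events in SAP 3.1.5 has no upper limit, so it can make an event treatment-emergent that 3.4.1.1 excludes on every possible day

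*SAP*

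**What the plan says.** SAP 3.1.5 opens its date rules with a general principle for AEs and concomitant medications: "the missing component(s) will be assumed as the most conservative value possible". For AEs with partial dates it then sets one test, which looks only at the first-dose boundary: "whether it can be conclusively established that the AE started prior to the start of study treatment or ended prior to the start of study" (the quote stops one word short of the end of its sentence). Where this test gives no firm answer, a default follows: "If the above cannot be conclusively established based on the partial and/or present dates, then the AE will be considered as treatment-emergent".

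SAP 3.4.1.1 defines a TEAE as an event starting on or after the first dose, within this limit: "up to 30 days past the last administration of study drug, or after 30 days past last dose and meeting one of the following criteria". The four criteria are a serious AE, an AE of special interest post-transplant, an AE related to study medication, and an AE related to HLA sensitization. The same section says that "AEs will be captured from the date of informed consent through study completion".

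The post-transplant schedule in Appendix A is narrower. It asks for all AEs up to 30 days after the last injection and, from day 31, only those considered related to study drug. Serious AEs and AEs of special interest have their own rows and run throughout.

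**The concern.** The TEAE definition has a lower boundary (first dose) and an upper boundary (last dose + 30 days, unless a late criterion is met). The partial-date rule tests only the lower one. Any event not shown to have started or ended before treatment becomes a TEAE, however late it is known to have begun.

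Two identical late events could then be classified differently because one has a full date and the other lacks its day. TEAE counts belong to a primary safety endpoint. A wrongly included non-serious, unrelated late event could enter the overview line for any TEAE and, depending on the event, the lines for Grade 3 or higher and for COVID-19, with the matching tables by system organ class and preferred term. It could not enter the lines for related, serious or special-interest events.

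**Working it through.** The SAP states no figure to reproduce, because this is a classification rule. The check applies both rules to the same events.

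**Rules as written**

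- 3.1.5: TEAE unless the latest possible start, or the latest possible stop, is before the first dose.
- 3.4.1.1: TEAE if first dose ≤ start ≤ last dose + 30 days, or if start > last dose + 30 days and one of the four criteria is met.

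**Worked case.** The calendar dates are illustrative. Day 56 is a third-dose day in Table 1 of SAP 2.2.1.

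- First dose: 6 Jan 2020.
- Last dose: 6 Jan + 56 days = 2 Mar 2020.
- Limit: 2 Mar + 30 days = 1 Apr 2020.

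Take a non-serious, unrelated AE, not of special interest, with month and year known, day missing, and no stop date before treatment:

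| Recorded start | 3.1.5 | 3.4.1.1, over every possible day |
|---|---|---|
| Dec 2019 | not TEAE | not TEAE on any day |
| Jan 2020 | TEAE | TEAE from the 6th, not before: open |
| Apr 2020 | TEAE | TEAE on the 1st, not after: open |
| Sep 2020 | TEAE | not TEAE on any of 30 days |

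In the January and April rows the known parts leave real doubt, and the default to TEAE is a fair worst-case choice. In the September row there is no doubt. Even the earliest possible day, 1 Sep, is 153 days after the limit (30 + 31 + 30 + 31 + 31, counting from 1 Apr to 1 Sep). Choosing the most conservative day in that month would not make the event a TEAE; only the default sentence does.

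**How often the known month settles the question.** Inputs: last dose on Day 28, 56 or 84 (Table 1); follow-up of about 15 months (SAP 2.2.1), taken as days up to 455; first-dose dates spread evenly over one year. For each day after the limit, ask whether its calendar month begins after the limit.

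| Last dose | Limit | Month wholly after limit | Month could straddle limit |
|---|---|---|---|
| Day 28 | Day 58 | 96.3% | 3.7% |
| Day 56 | Day 86 | 96.0% | 4.0% |
| Day 84 | Day 114 | 95.7% | 4.3% |

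These are shares of calendar days, not of events. They show that when only the day is missing, the known month nearly always decides the upper boundary.

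**Which recorded events are exposed.** Under Appendix A, events recorded from day 31 after the last injection are related, serious or of special interest. Each meets a late criterion of 3.4.1.1, so both rules agree. The conflict is confined to unrelated, non-serious events, not of special interest, that are recorded late anyway and lack a full start date. The wording in 3.4.1.1 on capture through study completion leaves room for them. The SAP does not state their number.

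**The case against.** The strongest reply is that the conflict is almost empty. Appendix A does not schedule recording of the events concerned, the study has no formal hypothesis testing (SAP 3.1.4), and 3.1.5 openly takes a worst-case approach. A sensible programmer might also treat the partial-date rule as settling only the lower boundary and then apply 3.4.1.1. Section 5 leaves detailed programming specifications to a separate document, which could say so.

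Much of this stands. It limits the point to a minor one, and it justifies keeping the TEAE default wherever the known parts leave doubt. It does not rescue the sentence. A worst-case principle resolves uncertainty, and a month wholly after the limit leaves none. Nothing in 3.1.5 makes the default subject to the 30-day limit.

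A reader might also infer a stronger problem at the transplant date. For an incomplete medication start, 3.1.5 says that "the first day of the month will be imputed for missing day and January will be imputed for missing month". Elsewhere, 3.4.2.1 states: "Duration of anti-viral therapy use is the total number of days of recorded post-transplant anti-viral use". Section 3.4.1.4 adds: "The pre- and post-transplant immunosuppressant use will be summarized by preferred term". From these one could conclude that post-transplant drugs will be moved to before the transplant or given negative times. The SAP does not support that. Section 3.1.5 confines this imputation to deciding whether a medication is prior or concomitant. Section 3.4.2.1 defines anti-viral use as following the recorded trigger, and measures time to the first post-transplant use. Misplacement would arise only if the imputed dates were reused outside their stated purpose. What remains is unspecified detail: the most conservative value has no stated direction for anti-viral timing or duration.

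**Conclusion.** Wrong as written, minor. Sections 3.1.5 and 3.4.1.1 give opposite answers for a non-serious, unrelated AE, not of special interest, whose known month lies wholly after last dose + 30 days and whose day is missing. The conflict follows from the text and needs no assumption about the data.

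Its size in events is unknown, since the SAP gives no count of partial dates. If recording follows Appendix A, few events should be affected. If AEs of every kind are recorded through study completion, as 3.4.1.1 reads, more could be. The figure of about 96% rests on evenly spread dates and describes calendar days only. No hypothesis test or sample size depends on the point, and no error at the transplant date is established.

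**What to change.** In SAP 3.1.5, keep the check that the AE did not start or end before the first dose, and restrict the default. Suggested sense: a partial-dated AE that cannot be shown to have started or ended before the first dose is treatment-emergent if the known parts of its start date allow a start on or before last dose + 30 days, or if it meets one of the late criteria of 3.4.1.1; otherwise it is not. An AE with no start date at all, or whose known month or year could straddle the limit, stays a TEAE under the stated worst-case approach.

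Optionally, add one sentence that the prior/concomitant imputation is not to be reused for anti-viral timing and duration or for pre-/post-transplant outputs.

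The cost is one or two sentences and one extra condition in the TEAE derivation. No new data are needed, and the change can be made before database lock, by which time Section 1 says the SAP will be final.

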3.2 Analysis Populations

3.2.1 *Intent-to-Treat (ITT) Population*

The Intent-to-Treat (ITT) Population will include all patients who are enrolled. For Group 1 and Group 2, enrolled will be defined as being randomized and patients will be analyzed by their randomized treatment group. For Group 3, enrolled will be defined as receiving at least one dose of study drug.

3.2.2 *Modified Intent-to-Treat (mITT) Population*

The modified Intent-to-Treat (mITT) Population will include all ITT patients who receive a kidney transplant and at least 2 doses of study drug prior to kidney transplant. The mITT Population will be used for all efficacy analyses and analyzed in the same fashion as the ITT Population.

3.2.3 *Immunogenicity Population*

The Immunogenicity Population will include all ITT patients who receive at least 1 dose of study drug and who have at least 1 post-dose immunogenicity measurement. The Immunogenicity Population will be analyzed in the same fashion as the ITT Population.

3.2.4 *Safety Population*

The Safety Population will include all patients in the ITT Population who receive any study drug and will be analyzed by their actual treatment group (if different than randomized).

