2.1.2 Secondary Objectives

- To assess the efficacy of the administration of at least 2 doses of HB-101 compared to that of placebo in mitigating CMV DNAemia/viremia for CMV seronegative (-) recipients awaiting kidney transplantation from a CMV seropositive (+) donor and followed by CMV preemptive therapy post-transplant.
- To assess the efficacy of the administration of at least 2 doses of HB-101 compared to that of placebo in decreasing the use of anti-virals at treatment dose for CMV seronegative (-) recipients awaiting kidney transplantation from a CMV seropositive (+) donor and to be treated prophylactically for CMV post-transplant.
- To assess the efficacy of the administration of at least 2 doses of HB-101 in CMV seropositive (+) recipients awaiting kidney transplant and followed by CMV post-transplant preemptive management or prophylactic anti-viral therapy.

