2.2 Study Design

2.2.1 Overview

This is a Phase 2 study of HB-101, a bivalent CMV vaccine, in patients awaiting kidney transplantation and includes a randomized, placebo-controlled portion (Groups 1 and 2) and an open-label portion (Group 3). Approximately 150 patients recruited globally from specified transplant centers will be enrolled. The study will occur at approximately 25 to 40 global sites.

A high-level study schematic of Study H-100-002 is presented in Figure 1.

Figure 1 High-Level Study Schematic

For Groups 1 and 2, adult CMV seronegative (-) patients awaiting kidney transplant from a CMV seropositive (+) living donor will be enrolled according to treatment intent with regard to the method of CMV prevention after transplant (either preemptive or prophylactic) as defined at study enrollment by the investigator and institutional standards.

Patients enrolled into Groups 1 and 2 should have a living donor kidney transplantation ideally planned between 2 to 4 months after the first injection of study drug (HB-101 or placebo).

- Group 1 - The preemptive group will be randomized in a 2:1 ratio (HB-101:placebo) to receive either HB-101 or placebo before transplant. Post-transplant patients will be monitored per preemptive institutional standards.
- Group 2 - The prophylactic group will be randomized in a 2:1 ratio (HB-101:placebo) to receive either HB-101 or placebo before transplant. Post-transplant patients will receive 3 to 6 months of anti-viral prophylaxis following institutional standards.

Enrollment of Group 2 will be limited to no more than 54% of total patients.

For Group 3, adult CMV seropositive (+) patients awaiting kidney transplant from a CMV seropositive (+) or CMV seronegative (-) living donor will be enrolled into Group 3. Post-transplant CMV management will follow either preemptive or prophylactic care as defined at study enrollment by the investigator and institutional standards.

Patients enrolled into Group 3 should have a kidney transplantation from a living donor planned between 2 to 4 months after the first injection of HB-101. Patients in Group 3 will receive HB-101 vaccination(s) prior to their transplant surgery. Enrollment of Group 3 will be a minimum of 15% of total patients.

Patients receiving at least 2 doses of study drug before transplant will be included in the statistical analysis of the efficacy endpoints.

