After Day 0 dose administration, the subsequent study drug administration(s) should be given 28 days (± 7 days) apart.

Patients whose planned transplantation is less than 35 days from the planned first study drug (HB-101 or placebo) injection should not be enrolled.

A minimum of 7 days (± 2 days) must be planned between the last dose of study drug and transplantation, unless agreed otherwise between the sponsor and investigator on a case-by-case basis.

Patients whose planned transplantation is no longer than 4 months from the time of the first study drug (HB-101 or placebo) injection should be enrolled. Changes in transplantation timelines will not result in patient withdrawal from the study. In case of delayed transplantation, additional study drug injections prior to transplantation can be discussed with the sponsor or sponsor designee (who should be blinded). The maximum allowed number of patients receiving additional study drug injections prior to transplantation will be capped at 10 patients (less than 10% of planned sample size).

For Groups 1 and 2, in the event that the living donor is not available and a kidney from a CMV seropositive (+) deceased donor becomes available, the patient can continue in the study after transplantation. For Group 3, in the event that the living donor is not available and a kidney from a deceased donor becomes available, the patient can continue in the study after transplantation.

The additional study drug booster will be administered at least 7 days (± 2 days) prior to the scheduled transplantation. This allows maximal protection against CMV prior to the transplant. Blood collection for immunogenicity will be performed prior to each study drug booster

administered. Immunogenicity will not be used to determine the administration of a booster as these results would be unblinding; instead, reactogenicity will be reviewed and the investigator and sponsor may decide not to administer the booster if there is evidence of increasing reactions with increasing number of vaccinations. The number and timing of vaccinations versus transplantation will be described in the descriptive analyses.

The schedule of events and Immunogenicity analysis and time points are listed in Appendix A.

2.2.2 *Randomization and Blinding*

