3.3.4 Demographic and Baseline Characteristics

Demographic characteristics (age, gender, etc.) and other baseline characteristics, including transplant characteristics, will be summarized for the ITT Population and repeated for other analysis populations (if different than the ITT Population).

The following demographic and baseline characteristics will be summarized:

- Age (years) at Informed Consent
- Sex
- Childbearing potential
- Race
- Ethnicity
- Height at screening (cm)
- Weight at screening (kg)
- Body mass index (BMI) (kg/m^2) at screening and BMI categories ($<30 \text{ kg}/\text{m}^2$, $\geq 30 \text{ kg}/\text{m}^2$)
- Baseline CMV quantitative PCR result
- Degree of human leukocyte antigen mismatch
- Use of induction therapy or not
- Relation of donor to patient
- Donor CMV serology
- ABO incompatibility
- Donor living status
- Warm ischemia time
- Cold ischemia time and unit
- Use of laparoscopy or not
- Side of kidney

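### The efficacy set for Groups 1 and 2 sets no condition on the CMV serostatus of the kidney actually transplanted, which can dilute the incidence estimates meant for Phase 3 planning

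*SAP*

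**What the plan says.** **Objectives.** SAP 2.1.2 has two placebo-controlled efficacy objectives. The first, for Group 1, is framed "for CMV seronegative (-) recipients awaiting kidney transplantation from a CMV seropositive (+) donor and followed by CMV preemptive therapy post-transplant". The second, for Group 2, has the same recipient and donor serostatus, with prophylaxis in place of preemptive care.

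**Entry.** In 2.2.1, "adult CMV seronegative (-) patients awaiting kidney transplant from a CMV seropositive (+) living donor will be enrolled" into Groups 1 and 2. Entry therefore rests on the planned donor.

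**Change of donor.** 2.2.1 foresees loss of the living donor. In Groups 1 and 2, if "a kidney from a CMV seropositive (+) deceased donor becomes available, the patient can continue in the study after transplantation". The parallel sentence for Group 3 sets no limit on the deceased donor's serostatus. For Groups 1 and 2 nothing is said about a seronegative replacement, and the 2.2.1 list of events that conclude a patient's participation does not name one.

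**Efficacy set.** In 3.2.2 the mITT Population is "all ITT patients who receive a kidney transplant and at least 2 doses of study drug prior to kidney transplant". The section adds: "The mITT Population will be used for all efficacy analyses". The donor is not mentioned.

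**Donor data.** 3.3.4 lists "Donor CMV serology" among the characteristics to be tabulated, and 3.4.1.4 states: "The CMV serology information will be summarized for transplant recipient and kidney donor". Neither section links donor serology to an efficacy summary.

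**The concern.** Enrolment, objectives and the donor-switch rule all treat a CMV-seropositive donor as part of what defines Groups 1 and 2. The efficacy set drops that element at the point where the actual donor becomes known. A seronegative recipient of a seronegative kidney (D-/R-) has no donor-transmitted CMV to prevent. Such a patient adds to the denominator of CMV infection, CMV disease and anti-viral use and will seldom add to the numerator, for a reason unrelated to the vaccine.

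If the donor-switch rule means that the patient does not continue, the patient still meets both mITT conditions but contributes almost no follow-up. The SAP gives no minimum follow-up and no censoring rule for the incidence summaries.

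At stake are the absolute incidences and risk differences, since 2.2.4 says that the efficacy point estimates are to help design and power Phase 3.

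**Working it through.** **Inputs from the SAP.** About 150 patients and 2:1 allocation in Groups 1 and 2 (2.2.4). Group 2 at most 54% and Group 3 at least 15% of the total (2.2.1). The SAP states no CMV event rate, effect size or share of CMV-negative kidneys, so it has no figure on this point to reproduce.

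**Arm sizes.** These are enrolled counts, so they are upper bounds for mITT.
- Groups 1 and 2 pooled, with Group 3 at its minimum: 150 × 0.85 = 127.5, about 85 HB-101 and 42 placebo.
- Group 1 alone, with Group 2 at its maximum and Group 3 at its minimum: 150 × (1 − 0.54 − 0.15) = 46.5, about 31 HB-101 and 15 placebo.

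**Assumptions.** Incidence in seronegative recipients of a seropositive kidney (D+/R-) is 50% on placebo and 25% on HB-101. Incidence in D-/R- is 0%. The share *f* of CMV-negative kidneys is 2% to 10%.

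**One misplaced patient, placebo arm at 50%.**
- Pooled arm of 42: 0.50 × 41/42 = 48.8%, a fall of about 1.2 points.
- Group 1 arm of 15: 0.50 × 14/15 = 46.7%, a fall of about 3.3 points.

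**Same share in both arms.** Observed incidence = (1 − *f*) × incidence in D+/R- + *f* × incidence in D-/R-.

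| *f* | Placebo | HB-101 | Risk difference (points) | Risk ratio |
|---|---|---|---|---|
| 0 | 50.0% | 25.0% | 25.0 | 0.50 |
| 2% | 49.0% | 24.5% | 24.5 | 0.50 |
| 5% | 47.5% | 23.75% | 23.75 | 0.50 |
| 10% | 45.0% | 22.5% | 22.5 | 0.50 |

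**Sensitivity at *f* = 10%.** With placebo incidence of 40% or 60% and risk still halved, the difference falls from 20 to 18 or from 30 to 27 points. If D-/R- incidence is 5% instead of 0%, the incidences are 45.5% and 23.0%, and the risk ratio is 0.505.

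**Chance imbalance.** Suppose there is no vaccine effect and both pooled arms have a true D+/R- incidence of 50%. Four CMV-negative kidneys, all in placebo, give 0.50 × 38/42 = 45.2%. All four in HB-101 give 0.50 × 81/85 = 47.6%. The spurious difference is 4.8 or 2.4 points, in either direction.

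**Does other text close the gap?** The extra tables in 3.4.2 for all transplanted patients have no donor condition. Analyses by transplant characteristics (3.4 and 3.4.4) are optional and depend on favourable results.

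**The case against.** The case for leaving the text alone has real weight.

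- **No literal contradiction.** The objectives speak of patients awaiting a seropositive donor, a status before transplant that every correctly enrolled Group 1 or 2 patient meets. A reader might infer that 3.2.2 contradicts 2.1.2. It does not, and analysis by status at enrolment can be defended.
- **Few cases.** By naming only a seropositive deceased donor, the donor-switch rule implies that other cases are not meant to continue. The protocol, not shown here, may deal with withdrawal. Two patients among 15 placebo would give 6.5/15 = 43%, but that is a 13% share, above the 10% taken here as the upper end.
- **No success endpoint.** A reader might infer that the SAP scores these patients as vaccine or placebo successes. It has no responder endpoint, only incidence and time to event, analysed as observed (3.1.5). That a patient with little follow-up enters as a non-event follows from the absence of a rule, not from a stated one. A D-/R- patient can also have an event.
- **No systematic bias and no error rate at stake.** Randomisation spreads the cases over both arms, and 3.1.4 plans no formal hypothesis testing.
- **The count would be visible.** Donor serology is tabulated, so a reader of the report could see how many such patients there were.

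These points limit the size of the problem without removing it. A table of donor serology does not give D+/R- incidences. The route that could is conditional on results, and 2.2.2 allows sponsor team members to be unblinded patient by patient after transplant. A later choice about these patients could therefore be made with the arm known.

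**Conclusion.** The point holds as a gap in a stated rule. Read literally, 3.2.2 keeps Group 1 and 2 recipients of a CMV-negative kidney in every efficacy denominator, although the objectives and the donor-switch rule concern seropositive donors.

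The effect is a downward dilution of absolute incidence and risk difference, in proportion to the share of such patients. At equal shares it leaves the risk ratio nearly unchanged and favours neither arm; in small arms chance imbalance can shift the contrast either way. The sizes in the working rest on assumed event rates and an assumed share of CMV-negative kidneys, and the true number may be zero. The point touches secondary, descriptive endpoints only. It is worth correcting because those estimates are meant to feed Phase 3 design and the remedy is cheap.

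**What to change.** Add to SAP 3.2.2, in substance: for Groups 1 and 2, CMV efficacy endpoints are summarised in mITT patients whose transplanted kidney came from a CMV-seropositive donor, judged by actual donor serology; patients who received a CMV-negative kidney are listed separately; the summary in the full mITT Population is kept as supportive.

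Reconcile this with the two parts of 2.2.1 that bear on it, the list of events concluding participation and the donor-switch rule, so that the status and follow-up of these patients can be read from one consistent text.

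The cost is a short addition and one population flag from data already collected. Donor serology is fixed before transplant and is not plausibly affected by blinded study drug, so the restriction should add no arm-related selection. The downside is small: a few patients may leave the main CMV tables.
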